12.2 Medical History

Standard medical history assessments will be conducted at Screening. Clinical centers should make every effort possible to obtain medical records to document the diagnosis of the applicable indication. At the screening visit, we will also ask about participation in previous investigational trials for the indication being treated in the study and the number of previous trials participated.

12.3 Medication History/Demographics and Concomitant Medications

At the screening visit subjects will be queried regarding concomitant medication use and medication history. Restricted medications were previously described in Section 9.6. Demographic information will consist of items such as age, race, gender, education, employment, smoking status.

12.4 Lesion Counts

All inflammatory and noninflammatory lesions will be counted by a clinical center investigator at each weekly visit.

12.5 Discoloration Review

Discoloration is an assessment of skin color change related to the study product color remaining on the skin. It will be reviewed by delegated clinical center staff at the weekly visits as reflected in Table 4.a and one of the options below will be selected.

Discoloration	None	Minimal	Moderate	Marked
----------------------	------	---------	----------	--------

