The Placebo will consist of a formulation containing the same excipients as the active drug product. The Placebo will be color-matched to the active study drug. Placebo will be supplied in 10 mL tubes. Formulation and packaging of the Placebo is done by Velesco Pharmaceutical Services, LLC.

Criteria for Evaluation:

Clinical Efficacy

Clinical effectiveness will be evaluated using the Five-scale IGA for Acne Vulgaris at baseline and end of study, Patient-reported outcomes, and counts of inflammatory and noninflammatory lesions.

Safety Assessments

Safety will be assessed via AE monitoring, concomitant medication monitoring, physical examinations, vital signs, clinical safety laboratory evaluations (complete blood count and chemistry), and pregnancy testing (if applicable).

Table 4.a Schedule of Observations and Procedures

Assessment	Screening ⁷	Treatment Period						Follow-up	
	Day -14 to Day -1	Baseline Day 1	Day 8 (+/- 2 days)	Day 15 (+/- 2 days)	Day 22 (+/- 2 days)	Day 28 ⁸	Day 29 (+/- 2 days)	Day 43 (+/- 2 days)	Follow-up ⁹
Informed consent	X								
Inclusion/exclusion criteria	X	X							
Medical history/demographics	X								
Concurrent medical conditions	X	X	X	X	X		X	X	
Medication history	X								
Concomitant medications	X	X	X	X	X		X	X	
Physical examination, including vital signs and weight ¹	X	X	X	X	X		X	X	
Height	X								
IGA ²	X	X	X	X	X		X	X	
Lesion Counts (Face)		X	X	X	X		X	X	
PRO questions ³			X	X	X		X	X	
Clinical safety laboratory assessments ⁴		X						X	
Urine pregnancy test ⁵	X							X	
Randomization *Part B only		X							
Dosing ⁶		X	X	X	X	X			
Discoloration Review			X	X	X		X	X	
Photographs (optional)		X	X	X	X		X	X	
Pre- and post-treatment AE monitoring	X	X	X	X	X		X	X	

¹ Includes sitting blood pressure, pulse rate and temperature.

² IGA is the 5-point scale as defined in this protocol.

³ All subjects will be asked questions regarding the study drug, clearing and color, these are the Patient Reported Outcome (PRO) questions (see Appendix A).

⁴ Clinical safety laboratory assessments will include CBC with differential and CMP.

⁵ Females of child-bearing potential must have negative results within 48 hours prior to start of drug treatment for inclusion. The Day 43 test is performed for females of child-bearing potential who receive at least one application of study drug.

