Studies have been performed using intravenous infusions of BMX-010 in multiple models including rats, mice, dogs, guinea pigs, and baboons with the finding of dose-related hypotension [5,6]. Redox-active metalloporphyrin compounds (such as BMX-010) are potent, catalytic antioxidants and have the potential to scavenge superoxide within the vascular system and thereby change the balance of superoxide and nitric oxide in the microvasculature. This would augment the vasodilating activity of nitric oxide and lead to hypotension [5,6]. This has been

found in animal models, but only as a transient side effect related to intravenous administration of the drug in doses orders of magnitude higher than that being considered for topical administration. Hypotension has not been identified in any animal model treated with BMX-010 by topical therapy or by subcutaneous injection.

Mild photosensitization is a possible side effect of BMX-010. While native porphyrins have been shown to be photosensitizers, the redox-active metalloporphyrins are not expected to show significant photosensitization. When native porphyrins are exposed to white light, the molecule can enter an excited state and on return to ground state emit fluorescent light, which is the cause for photosensitization. Redox-active metalloporphyrins such as BMX-010 contain a metal atom chelated into the middle of the porphyrin ring. The presence of this metal atom allows the molecule to give and take electrons and thus do redox chemistry. In the presence of white light, these redox-active metalloporphyrins would not be expected to enter an excitation state and would not be expected to emit fluorescence. A phototoxicity test in rabbits with BMX-010 demonstrated only weak phototoxicity with no test animals showing edema at any time point and 1 out of 5 animals exhibiting erythema at 24 hours and only very slight erythema at 72 hours. A summary of the possible adverse side effects that could be associated with BMX-010 administration is below. These possible side effects are dose-dependent, and the relatively low doses of this drug planned in this study have not been associated with side effects in animals other than those related to the color of the topically applied drug.

The most common side effects (expected to occur in more than 30% of subjects) are:

- Yellow to brown discoloration of the skin at the administration site which may take several days to resolve

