11.1 IGA

The Investigator Global Assessment (IGA) is a five scale (0 to 4) static evaluation of overall Acne Vulgaris severity (as described below). The change in IGA scores from Baseline through the final follow up visit will be assessed as endpoints in the study.

Drug treatment and efficacy assessment by IGA will be limited to the face. For a score of Clear, residual hyperpigmentation and erythema may be present.

Grade	Description
0 = Clear	No papules and/or pustules; no erythema
1 = Minimal	Rare papules and/or pustules; faint, up to but not including mild erythema
2 = Mild	Few papules and/or pustules; mild erythema
3 = Moderate	Pronounced number of papules and/or pustules, but less than numerous papules and/or pustules; moderate erythema
4 = Severe	Numerous papules and/or pustules, occasionally with confluent areas of inflamed lesions; moderate to severe erythema

There is no single, standardized grading system for severity of acne [20].

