12.6 Photographs

Photographs of the Acne Vulgaris optional based on subject consent and selection of specific clinical center participation by the sponsor. Photographs will be offered at each clinic visit.

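### Discoloration is defined as a colour change but has no pre-dose reference, so existing acne pigment may be graded as product stain, or stain dismissed as old marks

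*Protocol*

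**What the plan says.** Protocol Section 12.5 defines the item: "Discoloration is an assessment of skin color change related to the study product color remaining on the skin". Delegated site staff choose one of four levels: None, Minimal, Moderate or Marked. The section gives no rule for telling product colour from colour already in the skin.

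In Table 4.a the row reads "Discoloration Review X X X X X". By column position the five marks fall on Days 8, 15, 22, 29 and 43. Screening and Baseline Day 1 are empty. In the same table, IGA, facial lesion counts and optional photographs all have a Baseline entry.

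Three other sections bear on the point:

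- Section 10.2 opens its list of risks with "The most common side effects (expected to occur in more than 30% of subjects) are", and the first entry is "Yellow to brown discoloration of the skin at the administration site which may take several days to resolve".
- Section 11.1 says of the IGA: "For a score of Clear, residual hyperpigmentation and erythema may be present".
- Section 12.6 limits the photographs: "Photographs of the Acne Vulgaris optional based on subject consent and selection of specific clinical center participation by the sponsor".

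Sections 9.2.2.1 and 9.2.3.1 exclude transient yellow skin discoloration of up to 7 days from adverse events.

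**The concern.** A change is judged against a starting state, and here that state is not recorded. Every subject enters with facial acne at IGA 2 or more. The protocol itself accepts that such skin can carry residual pigment, and the stain it expects lies in the yellow-to-brown range. A member of staff who sees brown colour at Day 8 has to decide from memory, or by guessing, whether it was there before. The error can go either way: old marks graded as stain, or stain dismissed as old marks.

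The estimated frequency and duration of one of the most common expected side effects are at stake. Short-lived yellow discoloration is kept out of the adverse event tables. The colour questions in Appendix A ask about concern over the product's colour and about stained clothing or bedding, not about skin. The Section 12.5 grade is therefore the main scheduled record of transient skin staining. No later analysis can recover a pre-dose grade that was not collected.

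**Working it through.** **Reproducing a figure.** The protocol states no sample-size, power or error figure that bears on this item. Section 14.6 says the sample sizes have no statistical basis. There is nothing to reproduce.

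**Schedule by column (Table 4.a).**

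| Item | Baseline | D8 | D15 | D22 | D29 | D43 |
|---|---|---|---|---|---|---|
| Discoloration review | – | X | X | X | X | X |
| Lesion counts | X | X | X | X | X | X |
| Photographs (optional) | X | X | X | X | X | X |

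**Timing.** Dosing ends on Day 28 (Table 4.a, footnote 8). Day 43 ± 2 is therefore 43 − 28 ± 2 = 13 to 17 days off drug, beyond the stated 7 days. Day 29 + 2 is at most 3 days off drug. For a subject who doses to Day 28, Day 43 is the only scheduled review that can test the 7-day statement. Subjects who clear and stop early may have other off-drug visits (Section 7.2.1).

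**Illustration of size.** Inputs:

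- s = true stain rate = 30%, the lower bound implied by Section 10.2.
- b = share of unstained subjects whose existing marks are graded as stain. This is an assumption; the documents give no value.
- n = up to 100 active and 50 placebo in Part B (Section 9.1.1).
- Placebo is assumed not to stain.

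Observed active rate = s + (1 − s)b. Observed placebo rate = b. SE = √[p₁(1 − p₁)/100 + p₀(1 − p₀)/50], where p₁ and p₀ are the observed active and placebo rates.

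| b | Active | Placebo | Difference (points) | SE (points) |
|---|---|---|---|---|
| 0% | 30% | 0% | 30 | 4.6 |
| 10% | 0.30 + 0.70 × 0.10 = 37% | 10% | 27 | 6.4 |
| 20% | 0.30 + 0.70 × 0.20 = 44% | 20% | 24 | 7.5 |
| 30% | 0.30 + 0.70 × 0.30 = 51% | 30% | 21 | 8.2 |

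In Part A there is no placebo column, so the whole excess of 7 to 21 points stays in the estimate. I read Part A as all-active, as Section 9.4 and the text of Section 9.1.1 state, although the cohort list in Section 9.1.1 also names placebo there.

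In Part B the difference shrinks but remains 27/6.4 ≈ 4.2 to 21/8.2 ≈ 2.6 standard errors from zero.

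**Opposite error.** If a share d of truly stained subjects is dismissed as old marks and b = 0, the observed rate is s(1 − d). For d = 10% to 30%, again an assumption, that is 0.30 × 0.90 = 27% down to 0.30 × 0.70 = 21%. The direction of any net bias is therefore not fixed by the documents.

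**Day 43.** If no stain remains, s = 0 and the observed rate is b in both arms: 10 to 30 of 100 active subjects and 5 to 15 of 50 on placebo. The group comparison would show that this is not a drug effect. An individual subject's positive grade would remain unexplained.

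**The case against.** The strongest reply is that the blank Baseline cell follows from the definition. The item grades colour attributed to product. Before the first application there is no product on the skin, so the grade would be None for everyone. If staff apply the definition correctly, b = 0 and nothing is biased. Section 11.1 says only that pigment may be present at a score of Clear. It gives no frequency at entry and no evidence that staff would confuse the two. This stands. It limits the finding to a risk, and it means that a Baseline tick under the unchanged definition would add nothing. It does not remove the gap, because the definition asks for an attribution and supplies neither a reference nor a rule.

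The safeguards are also real:

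- **Part B placebo arm.** Randomization should balance existing marks on average. The protection is incomplete. The placebo cream contains iron oxides as colorant (Section 9.2.3.1) and may itself leave colour. The placebo gel is white and unmatched (Section 9.2.6), so a grader may infer the arm. A comparison of arms also does not settle any one subject's grade.
- **Day 43.** If the stated 7-day duration is right, this visit is a largely stain-free reference within the subject. It cannot both assume that duration and test it.
- **Adverse event recording.** Only transient yellow discoloration of up to 7 days is exempt. Longer-lasting discoloration falls outside the exemption and is open to recording under Section 13.1, so Section 12.5 is not the sole record of persistent discoloration.
- **Baseline photographs.** They help where they exist, but they depend on subject consent and on which centers the sponsor selects.

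A reader might infer that old marks and stain cannot be told apart at all, or that the side-effect rate will certainly be wrong. The documents support neither reading, for the reasons above.

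**Conclusion.** The gap is real and its consequence is conditional. The protocol defines discoloration as a change, schedules no pre-dose reference and gives no attribution rule, so misattribution in either direction is possible. Part A is most exposed because it is open and has no control. Next come individual positive grades at Day 43. The Part B comparison is partly protected.

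The size cannot be derived from the documents. The 37-51% observed rate holds only for 30% true staining with an assumed 10-30% misreading rate, and the matching Part B differences also assume a placebo that does not stain, which is doubtful for the cream. With correct attribution the bias is zero.

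Priority is minor. Discoloration appears in no primary or secondary objective, and no efficacy conclusion rests on it. How the grades are to be analysed may be set out in the SAP and is not part of this point.

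**What to change.** 1. In Table 4.a, add an X for Discoloration Review at Baseline Day 1.
2. In Section 12.5, state that pre-existing facial discoloration of any cause is graded None, Minimal, Moderate or Marked before the first application, and that staff refer to this grade when rating product-related discoloration at later visits.
3. Report post-baseline grades alongside the Baseline grade, not only as a subtracted change. On a four-level whole-face scale, subtraction could hide real stain in a subject who starts at Moderate or Marked.

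The Baseline item must cover colour of any cause. Under the present product-only definition it would be None for every subject.

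The cost is one extra CRF field at a visit where the face is already IGA-scored and lesion-counted. One limit remains: marks that form during treatment will still not be identified.

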12.6 Photographs

Photographs of the Acne Vulgaris optional based on subject consent and selection of specific clinical center participation by the sponsor. Photographs will be offered at each clinic visit.

12.7 Clinical Safety Laboratory Variables

12.7.1 Blood Tests

Fasting blood samples (following an at least 8-hour fast) will be collected during as shown in Table 4.a. Clinical safety laboratory tests will include complete blood count with differential and comprehensive metabolic panel.

12.7.2 Urine Tests

Urine pregnancy tests (beta-human chorionic gonadotropin [HCG]) will be performed for women of childbearing potential within 48 hours prior to the start of drug treatment and repeated on the last visit.

13 SAFETY

13.1 Adverse Events

An AE is any untoward medical occurrence in a subject receiving study drug and which does not necessarily have a causal relationship with this treatment. For this protocol, the definition of AE also includes worsening of any pre-existing medical condition. An AE can therefore be any unfavorable and unintended or worsening sign (including an abnormal laboratory finding), symptom, or disease temporally associated with the use of BMX-010, whether or not related to use of the BMX-010. Abnormal laboratory findings without clinical significance (based on the Principal Investigator's judgment) should not be recorded as AEs. But laboratory value changes that require therapy or adjustment in prior therapy are considered AEs.

From the time the subject signs the informed consent form through the Follow-Up Visit all AEs must be recorded in the subject medical record and CRF.

AEs will be assessed according to the CTCAE version 5, which has been harmonized to MedDRA (Medical Dictionary for Regulatory Activities) coding. If CTCAE grading does not exist for an AE, the severity of the AE will be graded as mild (1), moderate (2), severe (3), life-threatening (4), or fatal (5).

Attribution of AEs will be indicated as follows:

- Definite: The AE is clearly related to the BMX-010
- Probably: The AE is likely related to the BMX-010
- Possible: The AE may be related to the BMX-010
- Unlikely: The AE is doubtfully related to the BMX-010
- Unrelated: The AE is clearly NOT related to the BMX-010

13.1.1 Reporting of AEs

BioMimetix JV, LLC, should be notified of all treatment-related AEs on a regular basis (to be agreed upon by the study team and BioMimetix JV, LLC). Reports of these should be made to [name], PhD, at [contact] (cell).

13.2 Serious Adverse Events

An AE is considered "serious" if in the opinion of the investigator it is one of the following outcomes:

- Fatal
- Life-threatening
- Constitutes a congenital anomaly or birth defect
- A medically significant condition (defined as an event that compromises subject safety or may require medical or surgical intervention to prevent one of the three outcomes above).
- Requires inpatient hospitalization or prolongation of existing hospitalization
- Results in persistent or significant incapacity or substantial disruption to conduct normal life functions.

13.2.1 Reporting of SAEs

Only AEs that the sponsor and/or Principal Investigator determines to be serious, unanticipated, and related or possibly/probably (i.e., more likely than not) related to the research must be reported to the IRB. Those AEs will be submitted, according the following guidelines:

- Report within 24 hours of learning about any subject's death that was unanticipated and more likely related to the research than unrelated;
- Report within 5 business days of learning about any serious, unanticipated, and related or possibly/probably related AE;
- Report within 10 business day of learning about any other unanticipated problem or event that was more likely related to the research than unrelated.

The Principal Investigator is responsible for compliance with all applicable regulations pertaining to the reporting of AEs to the IRB. To ensure patient safety, each study treatment-related serious adverse event (SAE) will also be reported to the sponsor, BioMimetix JV, LLC, within 24 hours by the Principal Investigator. Follow-up information on these events shall also be reported to BioMimetix JV, LLC, within 24 hours of receipt. Follow-up information may include hospital admission records, discharge summaries and autopsy reports, where applicable. The sponsor must report to the Food and Drug Administration (FDA), in an Investigational New Drug (IND) safety report, any suspected adverse reaction that is both serious and unexpected. Before submitting this report, the sponsor needs to ensure that the event meets all three of the definitions contained in the requirement:

- Suspected adverse reaction (i.e., there is a reasonable possibility that the drug caused the AE)
- Serious
- Unexpected

If the AE does not meet all three of the definitions, it should not be submitted as an expedited IND safety report.

The sponsor is required to report to the FDA all IND Safety reports in writing within 15 days (7 days for unexpected fatal or life-threatening suspected adverse reaction). The FDA Form 3500A can be found on the FDA website, www.fda.gov. All other AEs will be reported to the FDA in the IND Annual Report.

In addition to the above mentioned reporting responsibilities, after discontinuation of the study, all SAEs considered to be drug related will be reported to BioMimetix JV, LLC, by the Principal Investigator.

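### Section 13.2.1 gives the sponsor a 24-hour report only for SAEs already called treatment-related, although the sponsor must itself judge causality; all other SAEs reach it with no deadline

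*Protocol*

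**What the plan says.** Three parts of the protocol bear on how a serious adverse event reaches the sponsor.

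- **Timed route (Section 13.2.1).** "each study treatment-related serious adverse event (SAE) will also be reported to the sponsor", and this is to happen "within 24 hours by the Principal Investigator". Follow-up information on these same events has a 24-hour limit too. The last sentence of the section, on SAEs after the study, is likewise restricted to events considered drug related.
- **Sponsor's own judgement (Section 13.2.1).** "Before submitting this report, the sponsor needs to ensure that the event meets all three of the definitions contained in the requirement". The first of the three is "Suspected adverse reaction (i.e., there is a reasonable possibility that the drug caused the AE". The sponsor's written report to the FDA is due "within 15 days (7 days for unexpected fatal or life-threatening suspected adverse reaction").
- **Untimed routes.** Section 13.1 requires every adverse event, from consent through the follow-up visit, to be entered in the medical record and CRF. Section 15.1 has the sponsor monitor the study. Section 15.3.1 gives it access to the electronic database, and Section 15.3.2 has the monitor verify source documents. Section 15.3.2 also allows data on paper. None of these sections sets a time limit.

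On attribution, Section 13.1 defines five levels, among them "Possible: The AE may be related to the BMX-010". The IRB paragraph of Section 13.2.1 describes reportable events as "related or possibly/probably (i.e., more likely than not) related".

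**The concern.** The order of the two causality judgements is the difficulty. The sponsor has to decide whether a reasonable possibility of causation exists, but it is told promptly only of events for which someone has already answered a similar question affirmatively. An SAE that a site regards as unlikely or unrelated is the kind on which a second, central opinion could differ, and it is the kind for which the protocol sets no deadline.

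The sponsor is also the only party placed to compare events between sites. The protocol allows up to 20 centers and up to 210 subjects, so a single site has little basis for recognizing that an event has occurred elsewhere. What is at stake is how soon the sponsor can make its own assessment of SAEs that the site did not attribute to the product.

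**Working it through.** The point depends on no sample size, power or error rate, and the protocol states no figure to reproduce. The check is a comparison of the text.

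**1. Is there any timed route to the sponsor for SAEs not called treatment-related?**

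| Section | Events covered | Time limit for reaching the sponsor |
|---|---|---|
| 13.1 | all AEs, entered in medical record and CRF | none |
| 13.1.1 | treatment-related AEs, notified regularly | interval left to agreement |
| 13.2.1, SAE report by the Principal Investigator | treatment-related SAEs | 24 hours |
| 13.2.1, last sentence (post-study) | SAEs considered drug related | none |
| 15.1, 15.3.1, 15.3.2 | whatever is in the CRF, database or source | none |

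Only one row carries a definite limit, and it is restricted by relatedness. The restriction recurs in 13.1.1 and in the post-study sentence, so it is a consistent rule and not a slip in one line.

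**2. Who makes the call that opens the 24-hour route?** Section 13.2.1 does not say outright. The Principal Investigator is the reporter, and the stopping rules in Section 7.2.1 give relatedness to the clinical center Principal Investigator. The natural reading is that the site decides. This is an inference, though a strong one.

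**3. What must the sponsor do in the same section?** Confirm all three criteria, causation among them, before an IND safety report. The IRB paragraph also lets the sponsor and/or the Principal Investigator determine relatedness. Where the sponsor is to exercise that judgement, it has to know of the event.

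**4. What happens to an SAE rated Unlikely or Unrelated?** It is entered in the CRF (13.1) and the sponsor can see it once it is in the database or found at monitoring. It therefore arrives, at an unspecified time.

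**5. How much can one site see?** At the stated maxima, 210 subjects / 20 centers = 10.5 subjects per center on average. Both figures are upper limits and the true ratio may differ, but it illustrates why cross-site comparison falls to the sponsor.

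**6. The IRB wording, taken separately.** Section 13.1 makes Possible mean that the event may be related. The IRB sentence in 13.2.1 equates possibly with a probability above one half. Two of the three bullets below it (the 24-hour death report and the 10-business-day report) repeat a more-likely-than-unrelated test, while the 5-business-day bullet keeps possibly/probably without that gloss. A site using the Section 13.1 scale cannot tell whether a Possible event qualifies for the IRB.

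**The case against.** A fair defence runs as follows. Section 13.2.1 can be read as successive steps: the site flags related SAEs, and the sponsor then verifies the flagged ones against three criteria. That sequence is coherent, and the wording on relatedness for the IRB allows either party to decide. The sponsor also has the CRF, database access and its own monitors. The protocol expects all other AEs to appear in the IND Annual Report, which presupposes that the sponsor receives them. The trial uses a topical product for at most 28 days.

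Much of this stands, and it rules out several stronger conclusions that a reader might draw:

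- *That SAEs called unrelated never reach the sponsor.* They do, through the routes above. The restriction affects speed, not access.
- *That the 7- or 15-day FDA limit would be missed.* The protocol does not say when that clock starts. If it starts when the sponsor becomes aware of the event or makes its determination, late receipt delays the report without breaching the limit.
- *That blinding is the cause.* Only Part B is blinded. Part A, up to 60 of the 210 subjects, is open label, and the restriction operates equally in both parts.
- *That the more-likely-than-not gloss keeps Possible SAEs from the sponsor.* The gloss is in the IRB sentence. The sentence on reporting to the sponsor does not carry it.
- *That the number of delayed SAEs can be stated.* The protocol gives no SAE rate from which to estimate it.

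What the defence does not answer is the absence of any deadline. A verification step applied only to pre-selected events is not an independent judgement on the remainder, and an untimed CRF entry, possibly on paper, does not do the work of a 24-hour report.

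**Conclusion.** The point holds as one of timing. Section 13.2.1 makes prompt notice to the sponsor depend on a prior causality call, while the same section assigns a causality judgement to the sponsor. For SAEs not called treatment-related, the sponsor's own assessment and its comparison across sites are delayed by an amount the protocol does not bound; they are not lost.

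The conclusion rests on one inference, that the site investigator decides whether an SAE is treatment-related, and on the finding that no other section sets a time limit. It needs no assumed event rate. The mismatch between the IRB wording and the Section 13.1 scale is a separate, smaller inconsistency that should be corrected on its own merits. Neither matter touches the design, the sample size or the efficacy analysis.

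**What to change.** 1. In the Section 13.2.1 sentence on reporting to the sponsor, delete the words that limit it to treatment-related events, so that every SAE goes to the sponsor within 24 hours together with the investigator's attribution on the Section 13.1 scale.
2. Make the same change in the last sentence of Section 13.2.1, so that post-study SAEs are not restricted to those considered drug related. That sentence also lacks a time limit, which could be stated at the same time.
3. Separately, reconcile the IRB paragraph with Section 13.1: remove or redefine the more-likely-than-not gloss and treat the bullets that repeat it in the same way, so that it is clear whether an event rated Possible is reportable to the IRB. Changing the parenthesis alone would leave the bullets inconsistent.

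The cost is a short amendment to one section and a small number of additional SAE reports from sites. Section 13.1.1, on routine notification of non-serious events, can stay as it is provided it is clear that 13.2.1 governs SAEs.

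### The only timed SAE route to the sponsor (Protocol 13.2.1) covers events already judged treatment-related, so the sponsor's own causality test cannot be relied on to run promptly

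*Protocol*

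**What the plan says.** Section 13.2.1 sets the route from site to sponsor: "each study treatment-related serious adverse event (SAE) will also be reported to the sponsor". The Principal Investigator has 24 hours to do this. Follow-up information, such as hospital and autopsy records, is also due within 24 hours of receipt, but only for those same events.

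The section then gives the sponsor its own test. Before filing an IND safety report, "the sponsor needs to ensure that the event meets all three of the definitions contained in the requirement". The three parts are seriousness, unexpectedness and a causality criterion: "Suspected adverse reaction (i.e., there is a reasonable possibility that the drug caused the AE"). Qualifying reports go to the FDA "in writing within 15 days (7 days for unexpected fatal or life-threatening suspected adverse reaction").

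Two other sentences govern what the sponsor is told. Under 13.1.1 the sponsor "should be notified of all treatment-related AEs on a regular basis", at an interval still to be agreed. The last paragraph of 13.2.1 limits reporting after discontinuation of the study to SAEs considered drug related.

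Section 13.1 defines five attribution grades: Definite, Probably, Possible, Unlikely (doubtfully related) and Unrelated (clearly not related). It also requires all AEs, whatever their grade, to be entered in the medical record and CRF. Section 15.3.1 gives the sponsor access to the electronic database and a monitoring role. Section 15.3.2 allows data on paper or in an eCRF.

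**The concern.** The sponsor's causality assessment sits behind the site's. The sponsor is asked whether there is a reasonable possibility of a drug cause, but the prompt, timed report arrives only if the investigator has already called the event related. If the investigator attributes it elsewhere, nothing in the protocol brings it to the sponsor by a stated time.

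This matters because only the sponsor sees all centers. The synopsis allows up to 20 centers, and Section 9.1.1 allows up to 60 subjects on active drug in Part A and up to 100 in Part B. At those ceilings that is (60 + 100) / 20 = 8 exposed subjects per center on average, and more if fewer centers open. In Part B the investigator is also blinded to treatment. An isolated event that looks incidental at one center may look different beside similar events elsewhere, but only if the sponsor receives them in time to compare. Dosing lasts at most 28 days and the last clinic visit is Day 43, so an untimed route can outlast a subject's treatment.

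**Working it through.** No figure in the protocol needs reproducing. The check lists every route by which an SAE can reach the sponsor and asks of each whether it is filtered on causality and whether it has a time limit.

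| Route | Section | Limited to related events? | Time limit stated? |
|---|---|---|---|
| SAE report, with follow-up information | 13.2.1 | Yes | Yes: 24 hours for each |
| Regular AE notification | 13.1.1 | Yes | No: interval to be agreed |
| SAE report after study discontinuation | 13.2.1, last paragraph | Yes | No |
| CRF entry and sponsor database access | 13.1, 15.3.1, 15.3.2 | No | No: neither entry nor review; paper allowed |

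1. **Active notification.** The first three routes are those in which the site tells the sponsor about an event. All three are limited to events considered related, and only the first has a clock.
2. **Passive route.** The fourth is open to every AE. It depends on when the site completes the form and when the sponsor looks, and the protocol fixes neither.
3. **Combination.** No route is both unfiltered and timed.
4. **Where the filter bites.** The term used for the 24-hour report is not tied to the grades in 13.1. Definite, Probably and Possible would naturally count as related, and Unrelated would not. Unlikely is open: doubtfully related is weaker than related, but it is not the same as clearly not related. Two sites could handle the same event differently and both follow the text.
5. **Threshold.** The IRB paragraph of 13.2.1 begins "Only AEs that the sponsor and/or Principal Investigator determines to be serious, unanticipated, and related or possibly/probably" and then glosses that last expression as more likely than not. The gloss belongs to IRB reporting. A site that carried it over to the 24-hour report would, however, hold back events that could still meet the sponsor's lower standard of a reasonable possibility.
6. **Follow-up.** The 24-hour follow-up duty attaches only to events already sent. If the sponsor finds an unreported SAE in the CRF, the protocol sets no time for obtaining the records needed to judge it.

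**The case against.** The strongest reply is that the sponsor is not cut off. All AEs are recorded from consent through follow-up regardless of grade, the sponsor has database access with edit rights and monitors the data, and AEs outside expedited reporting go into the IND Annual Report, so the sponsor is expected to hold them eventually. This stands. A reader might infer that an SAE called Unlikely or Unrelated never reaches the sponsor's test in time. The documents do not support that: the CRF route could deliver it promptly, but nothing ensures that it does. Nor do they show that an FDA deadline would be missed, since the text does not say when the 15 or 7 days start.

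A reader might also see two contradictory rules on who decides relatedness, because one sentence names the sponsor and/or the Principal Investigator. That sentence governs which events go to the IRB, and its and/or wording lets the investigator's call suffice. It does not conflict with the 24-hour rule. The point here does not need it, because the three-part IND test is given to the sponsor explicitly.

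A further stronger reading is that the protocol expressly excludes Unlikely events. It does not. Exclusion is a natural reading of an undefined term.

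Finally, one might want a number for the signals lost. The protocol gives neither a rate of drug-caused SAEs nor a rate at which sites would attribute them elsewhere, and Section 10.2 reports no toxicities identified in earlier studies. Any such figure would rest wholly on invented inputs and would not measure the loss, since events graded Possible or higher would naturally go to the sponsor within 24 hours anyway.

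**Conclusion.** The point holds as a weakness in a stated rule. It is neither a contradiction nor detail left to another document. The protocol gives the sponsor a causality test and regulatory deadlines, then makes the only timed supply of cases depend on the site's causality call, using a term it does not define against its own scale. For an SAE not called related, the sponsor's assessment cannot be relied on to run promptly.

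The size is qualitative: three of three active notification routes are filtered, and the one unfiltered route is untimed. The conclusion rests on two assumptions: that sites follow the text as written, and that no separate safety procedure, unseen here, requires all SAEs within a fixed time. It does not depend on how Unlikely is read, because Unrelated events lack a timed route on any reading. The change should be made because it is cheap and bears on subject safety.

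**What to change.** In Section 13.2.1:

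- Require each SAE, whatever the investigator's attribution, to be reported to the sponsor within the existing 24 hours, with the Section 13.1 grade stated on the report.
- Extend the 24-hour follow-up duty to all SAEs.
- Reword the last paragraph so that SAE reporting after study discontinuation is no longer limited to events already considered drug related.

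In Section 13.1.1, state that the limit to treatment-related events does not apply to serious events, which follow 13.2.1.

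Keep relatedness filters only for IRB and expedited FDA reports. For the latter, the sponsor's own assessment then works on a complete set of SAEs. Removing the filter from the 24-hour report also makes it unnecessary to define which grades count as related for that purpose.

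The cost is a few edited sentences and a few extra 24-hour forms for events that prove unrelated. Visits, sample size and analysis are unaffected.
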